15 RANDOMISATION AND BLINDING

15.1 Timing of randomisation

The NHSBT Hub Operations communicates any donor offers and the extent of any donor offers (i.e. does the offer include skin flaps) to the recipient centres.

If an organ becomes available for a consented participant but a skin flap is not donated, then the participant will not be randomised. They will not continue to participate in the study and will receive the lung as part of their routine clinical care outside of the study.

If the offer is accepted by the recipient centre and matched to a patient who has consented to take part in the SENTINEL study, the recipient centre will reconfirm study consent (Stage 2 Consent) with the recipient. If consent is given, the study team will randomise the participant to receive either the lung transplant alone or a lung transplant and skin sentinel transplant.

The outcome of the randomisation will be communicated to the relevant parties involved in coordinating the retrieval and transplant (this may include recipient centre, SN, NHSBT Hub Operations, NORS team and recipient transplant teams by the local study team/randomiser).

15.2 Randomisation procedure

Participants will be randomised via a centralised validated computer randomisation program through a secure (encrypted) web-based service, RRAMP (https://rramp.octru.ox.ac.uk), provided by the Oxford Clinical Trials Research Unit (OCTRU); accessed via the REDCap study database.

Participants will be randomised to one of the following treatment arms:

Arm	Details
Lung transplant with sentinel skin flap	Transplant of a skin flap of the same donor as
(SSF) transplant (intervention)	the lung, transplanted at the same time as
	lung transplantation.
Lung transplant only (control arm)	Lung transplantation in accordance with
	usual procedure.

The randomisation outcome is communicated as per the 'PATHWAY FOR ORGAN DONATION AND RETRIEVAL' detailed in APPENDIX 1 – pathway for organ donation and RETRIEVAL

Randomisation outcome will be communicated directly back to the recruiting site by the randomiser immediately after randomisation (with an e-mail confirmation of randomisation sent to the site Principal Investigator, and the central study office and anyone else requested by the site). The SN's and NHSBT central Hub operations will also be informed whether or not skin retrieval is also required.

15.3 Randomisation methodology

Consenting participants will be allocated randomly (1:1) to either lung transplant with SSF transplant or lung transplant only.

Allocations will be generated using permuted block randomisation, with varying block sizes, stratifying for recruiting centre.

The randomisation schedule(s) will be designed by the OCTRU study statistician and full details will be detailed in a study randomisation and blinding plan.

15.4 Justification for stratification factors

The randomisation schedule is stratified for centre to balance for differences in routine practice, particularly in terms of assessing lung rejection (clinical or biopsy).

15.5 Re-randomisation following non-transplant

Randomised patients (i.e. those that have consented to the study and been offered and accepted an organ) who do not receive transplantation will return to the waiting list and be re-randomised if they are offered lung and skin donation in the future. Patients will repeat stage 2 consent prior to randomisation and their HRQoL questionnaires will remain valid.

15.6 Back-up randomisation procedure

In case the web system fails, back-up emergency allocations will be prepared using sealed envelopes.

15.7 Blinding

Table 1 provides an overview of the blinding status of all individuals involved on the conduct and management of the trial.

Table 1: Blinding status of those involved in trial conduct and management

Role in trial	Blinding status	Additional information
Participants	Not blinded	It is not possible to blind due to nature of the intervention. Participants will be told their treatment allocation immediately after randomisation.
Site research staff including Principal Investigator	Not blinded	It is not possible to blind due to the nature of the intervention. Following randomisation, an email will be sent to the PI and/or member of the site research team performing the randomisation (as delegated) confirming treatment allocation.
Chief Investigator	Not Blinded	It is not possible to blind the Chief investigator as they may be the primary clinician for those participants recruited at their site, however they will be blinded to allocations for participants at other sites. In instances where serious adverse events are reported, the CIs will become unblinded (if not already) to complete the full causality assessment.
Database programmer	Not blinded	The database programmer is responsible for the management of RRAMP randomisation system and the REDCap database and will have access to all unblinded datasets within both systems.
SENTINEL Trial Management staff within the Surgical Intervention Trials Unit (SITU)	Not blinded	Trial Management staff within SITU will not be blinded to treatment allocations as site staff may require support for randomisation, or participants may contact the trial team directly. Serious Adverse Event reports will also be handled by the trial management team which will contain allocation information.
Data Management	Not blinded	Data management staff will have access to the unblinded datasets within the trial randomisation system and database to ensure data quality and undertake central monitoring activities.
Trial statistician and Senior Trial Statistician	Not blinded	The trial and senior trial statisticians will have access to treatment allocations or data needed for generating the Data Safety and Monitoring Committee (DMSC) closed reports and the final analysis.
Central laboratory staff	Blinded	Laboratory staff will only have access to the samples CRF – they will not be able to access trial allocations

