PROCEDURE	Pre- baseline	Baseline		3 months +/-4WKS	6 months +/- 4 WK	12 months +/- 4WKS	Rejection Event
Skin swab of flap (those randomised to the lung and sentinel skin flap group).			X ¹	X	X	X	Х
Skin flap biopsy (those randomised to the lung and sentinel skin flap group)*			X ¹	Х	Х	Х	Х
Recipient native skin swab microbiome sample (both groups)			X ¹	Х	Х	Х	Х
Blood sample (both groups)			X ¹	Х	Х	Х	Х

^{*}When taken, these samples will be divided into two and sent to both a local lab for immediate analysis and to Oxford for storage for later analysis.

^{**} All biopsies are sent to local lab for analysis until the end of the trial when they will be transferred to Oxford for analyis.

X¹ after transplant re-vascularisation.

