18.3 Sample handling for trial-specific samples analysed in a central laboratory

Sample handling (including any local processing) and storage will be managed according to separate written instructions/sample handling manual. Table 5 summarises the arrangements for collection, timings, and analytical laboratories responsible

Table 5: Study-specific samples analysed by a central laboratory

Sample Type	Type Time point Tests to be undertal	
		the sample
Skin flap biopsy	Baseline	Immunological studies
(those randomised to the	3 months post-transplant	including HOT panel, DSP,
lung and sentinel skin flap	6 months post-transplant	flow cytology,
group)	12 months post-transplant	immunohistochemistry
	Upon suspicion of rejection	
Skin swab of flap(those	Baseline	Microbiome analysis
randomised to the lung and	3 months post-transplant	
sentinel skin flap group)	6 months post-transplant	
	12 months post-transplant	
	Upon suspicion of rejection	

SENTINEL_Protocol_V1.1_27Apr2023.docx IRAS number: 318347 REC Reference: 23/LO/0248

Sample Type	Time point	Tests to be undertaken on the sample	
Swab of recipient native skin	Baseline	Microbiome analysis	
(both groups)	3 months post-transplant	,	
,	6 months post-transplant		
	12 months post-transplant		
	Upon suspicion of rejection		
Transplanted Lung biopsy	Baseline	Immunological studies	
(if taken)	3 months post-transplant	including HOT panel, DSP,	
	6 months post-transplant	flow cytology,	
	12 months post-transplant	immunohistochemistry	
	Upon suspicion of rejection		
Transplanted Lung Bronchial	Baseline	Microbiome analysis	
brushing or brochoalveolar	3 months post-transplant		
lavage or sputum	6 months post-transplant		
(if taken)	12 months post-transplant		
	Upon suspicion of rejection		
10 ml blood	Baseline	Cell free DNA analysis	
(both groups)	3 months post-transplant	RNA and gene expression	
	6 months post-transplant		
	12 months post-transplant		
	Upon suspicion of rejection		

Provision of sample collection packs

Sites will be provided with biological transport packs for the transport of blood, skin swab and skin flap samples to Oxford where they will be documented and stored with the trial code, trial patient identifier, and date. Sites will also be provided with 4 and 8mm skin punch biopsy instruments and sample collection tubes, microbiological swabs and transport tubes for the skin swabbing. Blood is collected and stored in Streck Cell-Free DNA blood collection tube and Tempus tubes.

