At each sample event either a single 8mm punch biopsy is cut in half, or two x 4mm punch biopsies will be taken. Both biopsies will be stored in formalin with one biopsy to be sent to Oxford for later analysis and one sent to the local histology laboratory for paraffin embedding and clinical reporting. These blocks may be useful for the mechanistic investigation later in the study.

The lung samples will be sent for fixation in formalin and paraffin embedding (FFPE) and clinical analysis at the local laboratory. At the end of follow up these samples will be sent to Oxford for storage for later analysis for the mechanistic studies.

Samples may be stored for up to 5 years by Oxford after conclusion of the clinical component of the trial, during which they will be analysed for the mechanistic component of the study. We can only analyse the samples for the mechanistic elements once the clinical outcomes are known as correlation to clinical progress is needed to select the samples for analysis and comparison.

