18.4 Labelling and confidentiality of trial-specific samples

Study-specific samples that are not requested and processed in the same manner as standard of care clinical samples will be labelled as study samples in accordance with the separate sample handling manual.

All samples sent to analytical laboratories will be labelled with the study code, study patient number, initials and date taken. Should a laboratory receive any samples carrying unique patient identifiers the recipient must immediately obliterate this information and re-label and report a data breach to the Trial Office.

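### Table 1 lists central laboratory staff as blinded, but flap-only samples sent under the same patient number show who received a flap

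*Protocol*

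**What the plan says.** Protocol section 15.7, Table 1, gives a blinding status for each role. Central laboratory staff are the only group with the status of blinded, and the reason given is that they see only the samples CRF and "they will not be able to access trial allocations".

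The sample flow is set out in Table 3 (section 17.1), Table 4 (section 18.1) and Table 5 (section 18.3):

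- Two sample types are confined to the flap arm: "Skin flap biopsy (those randomised to the lung and sentinel skin flap group" and "Skin swab of flap (those randomised to the lung and sentinel skin flap group". Both are due at baseline, 3, 6 and 12 months, and on suspected rejection.
- Two sample types are taken in every participant at the same time points: 10 ml of blood, and "Recipient native skin swab microbiome sample (both groups".
- Section 18.3 provides packs for "transport of blood, skin swab and skin flap samples to Oxford where they will be documented and stored", with the trial code, patient identifier and date.
- Section 18.4 fixes the label: "All samples sent to analytical laboratories will be labelled with the study code, study patient number, initials and date taken".

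On timing, section 18.3 adds: "We can only analyse the samples for the mechanistic elements once the clinical outcomes are known". Section 24.7 plans to split mechanistic outcomes by treatment group when they are collected in both arms, with confidence intervals to support simple group comparisons.

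**The concern.** Withholding the allocation list blinds a laboratory only if the material it receives does not show the arm. Here one of the two treatments produces its own tissue, and that tissue is sent to the laboratory under an identifier shared with the participant's other samples.

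What is at stake is the arm comparison on the shared sample types. Section 11 includes steps that involve judgement, such as choosing tissue for spatial profiling and regions of interest for single-cell work. If the arm can be inferred when such choices are made or assays are read, expectation can enter the result. A reader of Table 1 would suppose that this route is closed.

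**Working it through.** No sample size, power or event figure bears on this point, so there is no stated result to reproduce. The check sets the sections side by side.

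**1. What reaches Oxford, and under what label**

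| Sample | Arm | Sent to Oxford | Label |
|---|---|---|---|
| Flap biopsy | Flap only | Half of each biopsy | Number, initials, date |
| Flap swab | Flap only | Yes | Number, initials, date |
| Native-skin swab | Both | Yes | Number, initials, date |
| Blood | Both | Yes | Number, initials, date |
| Brushing, lavage or sputum | Both, where local practice | Part of sample | Number, initials, date |
| Lung biopsy | Both, where local practice | After follow-up | Number, initials, date |

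Sources: Tables 3 to 5 for arm and destination; section 18.4 for the label.

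**2. How often a flap recipient is marked.** Two flap-only sample types at four scheduled points give 2 × 4 = 8 scheduled items, plus any at suspected rejection. One is enough to mark the participant. Later removal of the flap does not undo this, because the first flap samples are taken on the day of transplant.

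**3. How a participant without a flap is recognised.** Blood and native-skin swabs arrive over the same visits with no flap item beside them. This is inference from absence, so it is weaker than step 2. A participant who stops giving samples (sections 17.6 and 18.9), or whose flap samples are missed, could be misread.

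**4. From flap receipt to allocation.** The target is 76 + 76 = 152 participants randomised and transplanted (section 24.2). Let k be the number allocated to a flap who receive lungs only. Section 17.10 has them cross over to the lung-only arm, while section 24.9 analyses them as allocated. They send no flap sample and look like controls. With complete samples, allocation would be inferred correctly for (76 − k) + 76 = 152 − k participants. The protocol does not give k.

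**5. Who sends nothing.** Of about 254 planned randomisations, 254 − 152 = 102 (102/254 = 40%) do not proceed to transplant. All central samples are taken at or after transplant, so these randomisations produce none. They are randomisations rather than people, since section 15.5 allows re-randomisation.

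**6. Which outcomes are touched.** Lung rejection, the primary outcome, is diagnosed clinically or by local pathology (section 16.8). The Oxford laboratory does the mechanistic work, which section 24.2 calls hypothesis generating and for which it makes no sample size calculation.

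**The case against.** The strongest reply is that the sentence in Table 1 is about system access and may be literally true: staff may have no route to the allocation records. That stands as far as it goes. But the status entered is blinded, which promises more than lack of access to a list. The samples CRF left open to them would presumably show sample type.

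A second reply is that handling detail belongs to a separate manual, which may provide for recoding. That is possible. Section 18.4 nevertheless fixes a linkable label for everything sent to an analytical laboratory, section 18.3 repeats a patient identifier for storage, and neither describes its removal before assay. An unseen manual cannot be presumed to override them.

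Third, the document names one laboratory but does not say that the same individuals handle every sample type, nor that the histopathologists in section 11 are the staff meant in Table 1. That also stands: inference is possible, but it is not shown that every reader of an assay will make it.

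Fourth, the work is exploratory and does not guide care (section 18.7). This limits the importance of the point. It does not remove the conflict, because section 24.7 still plans comparisons by arm.

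A reader might also infer that blinding to rejection status is broken, since samples are selected once outcomes are known. Table 1 promises no such blinding, and section 11 makes rejection against non-rejection a comparison of interest. Section 18.3 does not say that those running the assays see the outcomes.

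**Conclusion.** Table 1 is wrong as written. The sample flow lets the central laboratory infer flap receipt, and hence allocation for nearly all transplanted and sampled participants. That wording assumes that k is small and that most scheduled samples arrive; the protocol gives no figure for either.

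Three stronger readings are not supported. Allocation is not visible for every participant: crossovers look like controls, missing samples blur the picture, and those not transplanted send nothing. The primary outcome is not affected by this point, because rejection is diagnosed at the sites. And nothing in the document says that the final report will claim blinded measurement; the trial is described as open-label throughout.

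The consequence is limited to exploratory mechanistic outcomes compared by arm. The size of any reading bias cannot be derived from the document. This is a minor point, but a real one and cheap to correct before assays begin.

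**What to change.** 1. For sample types common to both arms (blood, native-skin swab, lung biopsy, brushing, lavage or sputum), replace the patient number and initials with a per-sample assay code before assay. The trial office holds the key until results are locked. Because samples are selected on clinical outcome, codes can be issued after selection. Where the assay does not need the date taken, it is better kept with the key, since samples from one visit share it.

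2. Amend Table 1 to say that laboratory staff have no access to allocation records, that blinding to arm applies only to the coded common samples, and that flap samples cannot be masked as to flap receipt.

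3. Bring section 18.4 and the sample handling manual into line.

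The cost is a recoding list and some relabelling by existing staff, with no extra sample, visit or assessor. If recoding is not wanted, Table 1 should at least state that the laboratory is not blinded to flap receipt. Reading samples blind to rejection status and running them in random batch order are optional good practice, not corrections of an error in Table 1.

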15.8 Code break/ unblinding

Not applicable as there is no unblinding required. A pre-specified statistical analysis plan will be written in advance of un-blinding the data and any comparative analyses.

16 STUDY INTERVENTION AND COMPARATOR

16.1 Procedure for organ transplantation

NHSBT provide a blood and transplantation service to the NHS, looking after blood donation services in England and transplant services across the UK. This includes managing the donation, storage and transplantation of blood, organs, tissues, bone marrow and stem cells, and researching new treatments and processes (https://nhsbt.nhs.uk).

The National Organ Retrieval Team (NORs) will retrieve the lung in accordance with their usual care protocols and the skin flap will be retrieved by a dedicated SENTINEL study-specific skin flap retrieval and transplant team.

The SENTINEL study-specific plastic surgery retrieval and transplant team will generally be available 24 hours a day/7 days a week for timely travel to the donating hospital anywhere in the UK. They will be responsible for the retrieval of the donated skin flaps which will be performed at the same time as the lung retrieval at the donating hospital. The skin flap will be transported to the recipient hospital transplant unit, and then simultaneous surgical transplantation of the skin flap and lung will take place. Each completed episode will take on average 12-24 hours. The SSF retrieval will not be permitted to interfere nor delay retrieval or transport of the other organs.

16.2 Dedicated skin flap retrieval and transplant team

The dedicated study-specific skin flap retrieval and transplant team will consist of plastic surgeons and senior plastic surgery trainees familiar with performing radial forearm flaps. Radial forearm flaps are identical to the SSFs used in this study and are a common flap performed in plastic surgery. The dedicated skin flap retrieval and transplant team will be trained in the retrieval process and inset transplant process in part by attending the NHSBT masterclass in retrieval. This is a cadaver and classroom-based training course at which the Chief Investigator has taught for a number of years. The team will be deployed to donor hospital sites to retrieve SSFs from transplant donors for the study.

The skin flap retrieval and transplant team will be geographically dispersed so as to be able to cover all the hospitals in England and Wales at which retrievals may occur. The transplant team will be based at the transplanting hospitals, apart from Harefield which does not have an onsite plastic surgery unit and will be supplied by the plastic surgery team from Oxford. Backup support and supervision will be performed by the Chief Investigator, [name]; as well as a core plastic surgery team all of whom will have an honorary contract at all 5 transplant hospitals.

The SSF will be taken to support the organ transplantation. In these circumstances, retrieval of such tissues that are essential to re-establishing functionality in the recipient is covered by the same licence as retrieval of organs for implantation. This is discussed in more detail within the HTA's framework document in paragraphs 54 - 57. Although retrieval of SSFs is covered by the same retrieval licence under which organ retrieval takes place, we would request each licence holder to advise the HTA so that their records can be updated.

A Flow Chart of the process from NHSBT receiving an offer of organ donation to the retrieval of the organs is provided in APPENDIX 1 – pathway for organ donation and RETRIEVAL.

The SENTINEL skin flap retrieval and transplant team will have a single contact number through which they will be contacted when an offer of skin and lung has been received, to ensure that a retrieval team are available. The team receiving the call will coordinate retrieval and transplant process as follows: The offer, once accepted by the recipient site will be checked to determine whether the proposed recipient has consented to participate in the study. If they have consented to participate and are cross-matched appropriately, consent will be confirmed, and then the patient will be randomised.

If a participant is randomised to receive skin as well as lung, the study-specific skin flap retrieval and transplant team will liaise with the lung NORS team and attend alongside them to retrieve the skin flap. Either the same plastic surgery team who removed the skin flap or the local recipient site plastic surgery team will attend the transplant procedure and inset the skin flap.

16.3 Management of skin retrieval

Not all lung donor families will agree to the donation of a skin flap as well. In order to avoid waste of retrieved, under-utilised skin flaps, the availability of both lung and skin donation must be confirmed prior to the randomisation. If the patient is randomised to lung only, the skin flap will not be retrieved. If the patient is randomised to lung and skin then both organs will be retrieved.

Around 50% of the time, the offer of the lung transplant is rejected by the transplant team as the lung is unfit for transplant. This decision could possibly be made as late as after randomisation has been performed and retrieval has already commenced. If skin flap retrieval has commenced prior to the decision not to proceed with lung retrieval and transplantation then the skin flap will be aesthetically sutured in place on the donor forearm and dressed. Obviously, the transplant and intervention cannot occur and the patient will return to the transplant waiting list. The patient will not retain their randomisation, as the next offer they receive may not include the offer of skin. They will need to be newly randomised next time, but only if their next offer has also agreed to skin flap donation. If the decision is made at the recipient hospital, then both lung and skin flap will follow NHSBT policy and either be offered for research (if the donor family had consented for this) or discarded.

